## 1 BACKGROUND AND RATIONALE

CA2097A8 is an open-label, randomized, non-comparative Phase 2 study assessing nivolumab, plus abemaciclib (per original protocol) or palbociclib, and anastrozole as either concurrent or phased neoadjuvant treatment for men and postmenopausal women with primary breast cancer (BC)  $\geq 2$  cm that are estrogen receptor-positive (ER+) and human epidermal growth factor receptor 2-negative (HER2-) with safety run-in. As of Revised Protocol 03, abemaciclib related cohorts will no longer be investigated in this trial.

Nivolumab (BMS-936558) is a fully human, IgG4 (kappa) isotype monoclonal antibody (mAb), an immuno-oncologic (IO) checkpoint inhibitor that binds programmed cell death-1 (PD-1) on activated immune cells and disrupts engagement of the receptor with its ligands programmed death-ligand 1 (PD-L1; B7-H1/CD274) and programmed death-ligand 2 (PD-L2; B7-DC/CD273), thereby abrogating inhibitory signals and augmenting the host anti-tumor response. Abemaciclib and palbociclib are orally bioavailable and highly selective small-molecule inhibitors against cyclin-dependent kinases (CDK)4/cyclin-D1 and CDK6/cyclin-D3 enzyme complexes, lead to reactivation of retinoblastoma (Rb) protein, binding back of E2F transcription factor and subsequent cell cycle arrest, thus abrogating endocrine-resistant cell proliferation. Anastrozole is a reversible, third-generation, selective nonsteroidal aromatase inhibitor (NSAI) that reduces peripheral estrogen synthesis by blocking the conversion of androgens to estrogens in non-ovarian tissues. A detailed description of the chemistry, pharmacology, efficacy, and safety of the study treatments is provided in the Investigator Brochures (IBs) and package inserts.

The study will assess the efficacy and safety of: i) concurrent therapy with nivolumab in combination with palbociclib, and anastrozole (Arm A), ii) phased therapy with one initial priming cycle of palbociclib and anastrozole followed by nivolumab in combination with palbociclib, and anastrozole (Arm B), and iii) control treatment with palbociclib and anastrozole (Arm C). Participants with newly diagnosed, previously untreated primary ER+ and HER2- BC  $\geq 2$  cm will be subjected to a total 5 cycles (4 weeks per cycle) of neoadjuvant therapy before definitive surgery. Efficacy will be measured by significantly improved residual cancer burden (RCB) 0-I rate. [REDACTED]

PD-1 pathway inhibition has demonstrated clinical activity across multiple tumor types, including BC. An accumulating body of evidence supports PD-1/CDK4/6 blockade potential synergy, as it has become more apparent that CDK4/6 inhibitors modulate the tumor immune microenvironment (ie, increases expression of PD-L1, enhances antigen presentation and secretion of cytokines from both tumor and CD8+ T cells, and suppresses proliferation of immunosuppressive regulatory T cells [Tregs]). Preliminary clinical data in support of synergistic activity of the combination of pembrolizumab and abemaciclib has been demonstrated in a Phase 1b study on heavily pretreated participants with metastatic hormone receptor-positive (HR+), HER2- BC. Clinical data on combinations of other CDK4/6 inhibitors with PD-(L)1 blocking agents are being generated in multiple clinical trials spanning from the neoadjuvant to metastatic setting (ClinicalTrials.gov: NCT03573648, NCT02778685, NCT03294694). Additional treatment benefit (improved anti-

tumor efficacy and complete tumor regression) was observed in a syngeneic mouse tumor model by priming the anti-cancer immune response with abemaciclib in a phased administration of abemaciclib and an anti-PD-L1 therapy. Therefore, an additional phased therapy arm has been added for each CDK4/6 inhibitor to explore possible treatment benefit in patients.

The aim of the CA2097A8 study is to assess the potential synergistic activity of nivolumab, with palbociclib, and anastrozole in participants with newly diagnosed, previously untreated primary ER+, HER2- BC  $\geq 2$  cm, defined by significantly improved RCB (0-I) rate. [REDACTED]

[REDACTED] Additional objectives of the study include characterization of safety and tolerability [REDACTED]

### **Research Hypothesis:**

The combination of nivolumab, with palbociclib, and anastrozole is a safe and effective neoadjuvant treatment for patients with ER+, HER2- primary BC  $\geq 2$  cm.

### **Schedule of Analyses:**

An analysis will be conducted when enrollment to the safety run-in phase is completed and all patients have completed at least one cycle of study treatment (1 cycle = 4 weeks) and have been followed up for an additional 4 weeks or discontinued from the study prior to that in order to support the dose selection for the randomized phase.

Final analysis will be conducted when all participants in the Randomized Phase are treated and evaluated in terms of RCB and pCR and completed the study, including the follow up phase, or discontinued from the study prior to that.

## **2 STUDY DESCRIPTION**

### **2.1 Study Design**

This randomized, open-label Phase 2 study was to evaluate whether the combination of nivolumab, with abemaciclib or palbociclib, plus anastrozole is a safe and effective neoadjuvant treatment for men and postmenopausal women with primary BC  $\geq 2$  cm that is ER+ and HER2- subtype who are suitable to receive NET and willing to undergo SOC breast surgery after completion of the study treatment.

[REDACTED]

[REDACTED]

At implementation of Revised Protocol 03, the study will only evaluate whether the combination of nivolumab, with palbociclib, plus anastrozole is a safe and effective neoadjuvant treatment for men and postmenopausal women with primary BC  $\geq 2$  cm that is ER+ and HER2- subtype who are suitable to receive NET and willing to undergo SOC breast surgery after completion of the study treatment. Participants must have histologically confirmed invasive breast carcinoma meeting the characteristics described in Section 6.1 of protocol (Inclusion Criteria). Participants in screening and not yet treated were offered the option to join the safety lead-in of the nivolumab + palbociclib + anastrozole arm. Participants on treatment with nivolumab + abemaciclib + anastrozole were to be re-consented and continue on anastrozole alone, or taken off study. In addition, baseline chest Xray and periodic pulse oximetry were implemented to monitor ILD/pneumonitis in patients who will be treated with nivolumab + palbociclib + anastrozole.

The study is divided into 3 periods: Screening Period, On-treatment Pre-surgery (neoadjuvant) Period (Safety Run-in Phase and Randomized Phase), and Safety Follow-up Period.

The study will start with a Safety Run-in Phase for the combination of nivolumab, with abemaciclib or palbociclib, plus anastrozole and will begin the Randomized Phase after the regimen is determined to be safe. Participant assignment will be carefully managed by the study team with the Investigator in the Safety Run-in Phase to ensure equal distribution of participants in both cohorts (abemaciclib or palbociclib). The abemaciclib cohort (cohort 1) was closed after two participants were dosed per Revised Protocol 03. No further investigation of abemaciclib related arms is planned in the Randomized Phase. Participants in the Safety Run-in Phase will move to the Safety Follow-up Period upon completion of the neoadjuvant treatment or upon discontinuation. Potential needs for additional enrollment or for dose de-escalation will be discussed with Investigators and BMS during the Safety Run-in Phase. Once a safe dose for each regimen has been determined by BMS in collaboration with Investigators, the Randomized Phase of the study will begin.

[figure not shown]
In the Randomized Phase, participants will be randomly assigned by an IRT system to 3 different treatment arms and stratified by the following factors: [REDACTED]

[REDACTED] 2) evaluation of lymph nodes (cytologically positive vs radiologically or cytologically negative); and 3) tumor size ( $> 3$  cm or  $\leq 3$  cm).

For both the Safety Run-in Phase and Randomized Phase, participants will be treated for a maximum of 5 cycles (1 cycle = 4 weeks). Participants with progressive disease prior to completion of the 5-cycle study treatment must discontinue all study drugs and proceed to the Safety Follow-up Period. Participants who permanently discontinue the study drugs for any reason are considered to have completed the On-treatment Pre-surgery (neoadjuvant) Period, and hence reach end of treatment (EOT). After Cycle 5 or EOT, participants must continue to receive anastrozole (as concomitant medication and not as study treatment) until subsequent SOC breast surgery. Following the completion of neoadjuvant treatment, all participants who remain operative

candidates will undergo definitive surgery for BC within 4 weeks of the last neoadjuvant treatment administration. If anastrozole can no longer be administered after EOT, participants will go to breast surgery right away. Pre-surgical lymph node biopsy is not allowed. Information on the type of the surgery will be collected and recorded in the electronic case report form (eCRF). Surgical specimens will be collected for the analyses outlined in the protocol. Depending on treatment assignment, up to 2 safety follow-up visits will be conducted in person. The first safety follow-up visit (FU1) will be completed for all participants within 30 days ( $\pm 7$  days) from the last study treatment (oral or intravenous [IV], whichever occurs later). The second safety follow-up visit (FU2) will occur approximately within 100 days ( $\pm 7$  days) from the last dose of nivolumab and will be required for participants in the Safety Run-in Phase and participants randomized to Arms A and B in the Randomized Phase. Further planned treatment of participants in the adjuvant setting (i.e., radiotherapy, endocrine treatment, chemotherapy or any other treatment modality) will be at the discretion of the treating physician, following local clinical guidelines, and collected in the appropriate eCRF. The study design schematic is presented in [Figure 2.1-1](#).

**Figure 2.1-1: Study Design Schematic**

Abbreviations: Abema = abemaciclib; ANZ = anastrozole; BID = twice daily; cm = centimeter; ECOG = Eastern Cooperative Oncology Group; ER+ = estrogen-receptor-positive; FU1 = follow-up visit 1; FU2 = follow-up visit 2; HER2- = human epidermal growth factor receptor 2-negative; IV = intravenous; mg = milligram; N = number; Nivo = nivolumab; Palbo = palbociclib; PO = per os (by mouth); PS = performance status; Q4W = every 4 weeks; QD = once daily; Rand = randomized; wk = week.

a FU1 begins at the end of study treatment.

b Cytologically positive vs radiologically or cytologically negative.

- c At the time of Revised Protocol 03, 2 participants had been treated in Cohort 1 (nivolumab + abemaciclib + anastrozole), which was subsequently closed for enrollment.
- d At time of Revised Protocol 03, the decision was made to no longer evaluate abemaciclib in combination with nivolumab plus anastrozole; thus, the abemaciclib-containing combination arms have been removed from the Randomization Phase of the study.

## 2.2 Treatment Assignment

CA2097A8 is an open-label, randomized trial. After the participant’s initial eligibility is established and informed consent has been obtained, the participant must be enrolled into the study by calling the IRT to obtain a participant number. Every participant that signs the informed consent form must be assigned a participant number in IRT.

### Safety Run-in Phase

Participants will receive either abemaciclib in combination with nivolumab plus anastrozole (Cohort 1) or palbociclib in combination with nivolumab plus anastrozole (Cohort 2). Participant assignment will be carefully managed by the study team with the Investigator in the Safety Run-in Phase to ensure equal distribution of participants in both cohorts (abemaciclib or palbociclib). As per Revised Protocol 03, Cohort 1 (abemaciclib + nivolumab + anastrozole) was closed permanently. For cohort 2, 3 DLT-evaluable participants will be treated with the below starting doses:

- Nivolumab: 480 mg every 4 weeks (Q4W) intravenously (IV)
- Palbociclib 125 mg (once daily; QD) PO for 3 weeks of each cycle (1 week off)
- Anastrozole: 1 mg QD PO

If any DLT evaluable participants experiences DLT during DLT period, a lower dose of Palbociclib will be tested using a 3 + 3 schema. If no participants (0 of 3 DLT-evaluable participants) experience a DLT during the DLT period (4 weeks), the Randomized Phase will be initiated at this dose level. If 1 evaluable participant (1 of 3 DLT-evaluable participants) experiences DLT, then the cohort will be expanded to 6 DLT-evaluable participants. If no more DLTs are observed (1 of 6 DLT-evaluable participants), then the Randomized Phase will be initiated at the dose level tested. If 1 or more additional evaluable participants (2 of 6 DLT-evaluable participants) experiences DLT during the DLT period, a lower dose will be tested using the same 3 + 3 schema.

The recommended abemaciclib dose modifications for adverse reactions are provided in Table 2.2-1. Discontinue abemaciclib for participants unable to tolerate 50 mg BID.

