If no participants (0 of 3 DLT-evaluable participants) experience a DLT during the DLT period (4 weeks), the Randomized Phase will be initiated at this dose level. If 1 evaluable participant (1 of 3 DLT-evaluable participants) experiences DLT, then the cohort will be expanded to 6 DLT-evaluable participants. If no more DLTs are observed (1 of 6 DLT-evaluable participants), then the Randomized Phase will be initiated at the dose level tested. If 1 or more additional evaluable participants (2 of 6 DLT-evaluable participants) experiences DLT during the DLT period, a lower dose will be tested using the same 3 + 3 schema. See [Figure 5.1.2.1-1](#) for an overview of the 3 + 3 approach to be used for the Safety Run-in Phase.

Figure 5.1.2.1-1: Schematic of Safety Run-in Phase 3 + 3 Approach

Abbreviations: DLT = dose-limiting toxicity.

^a For additional details see [Section 7.4](#) (Dosage Modification).

Continuous evaluation of toxicity events will be performed. If at any time, the aggregate rate of treatment-related toxicities meeting DLT criteria exceeds 33% across participants treated in a cohort, the findings will be discussed with the Investigators and further enrollment may be interrupted. Any toxicities that occur beyond the DLT period will be accounted for in making final dose level decisions.

Generally, if a cohort is discontinued due to DLT of unclear relevance to nivolumab, a lower dose level of CDK4/6 inhibitor per product label will be tested in the next cohort. See [Section 7.4](#) (Dosage Modification) for additional details on permitted dose adjustment. If a cohort is discontinued due to DLT related to nivolumab, a different dose or dose schedule will be explored per Investigator and Medical Monitor discussion.

For cohort expansion or dose de-escalation decisions, the available toxicity information (including AEs and laboratory abnormalities that are not DLTs), clinical judgment [REDACTED] will be evaluated by the Investigators and BMS study personnel (including the Medical Monitor and statistician) during a dose decision meeting by teleconference. Drug administration at the next dose level or proceeding to the Randomized Phase must not occur until the Investigator receives written confirmation from BMS indicating that the results of the previous dose level were evaluated and that it is permissible to proceed.

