^a For palbociclib, the starting dose level will be the safe dose determined upon completion of the Safety Run-in Phase.

^b After 5 cycles or EOT, all participants should continue to receive anastrozole until breast surgery. Anastrozole is not considered study therapy beyond completion of Cycle 5 or EOT.

Randomized participants should begin study treatment within 3 calendar days of randomization.

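### SAP 2.2 lowers the palbociclib dose after any DLT, contradicting the 1-of-3 and 1-of-6 rules in the same paragraph and in Protocol 5.1.2.1

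*SAP*

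**What the plan says.** SAP 2.2 (Treatment Assignment, Safety Run-in Phase) gives the Cohort 2 starting doses for 3 DLT-evaluable participants and then states: "If any DLT evaluable participants experiences DLT during DLT period, a lower dose of Palbociclib will be tested using a 3 + 3 schema".

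The same paragraph continues with four specific branches:

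- 0 of 3: the trial moves on to the Randomized Phase at the current dose.
- 1 of 3: "If 1 evaluable participant (1 of 3 DLT-evaluable participants) experiences DLT, then the cohort will be expanded to 6 DLT-evaluable participants".
- 1 of 6: the Randomized Phase starts at the dose tested.
- 2 of 6: "a lower dose will be tested using the same 3 + 3 schema".

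Protocol 5.1.2.1 has the same four branches. At 1 of 6 it says: "If no more DLTs are observed (1 of 6 DLT-evaluable participants), then the Randomized Phase will be initiated at the dose level tested". It contains no rule that lowers the dose after any single DLT.

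The result of the run-in carries forward. Footnote a of Protocol Table 7.1-2 says: "For palbociclib, the starting dose level will be the safe dose determined upon completion of the Safety Run-in Phase". Palbociclib is given in Arms A, B and C.

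**The concern.** The sentence has its own trigger (at least one DLT) and its own action (go to a lower dose). With exactly one DLT among the first three, it says to step down, while the branches say to stay at the dose and enrol three more. Both cannot be followed.

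At stake is the palbociclib starting dose for all three randomised arms, control included. The SAP also defines an analysis specifically to support that dose choice (Schedule of Analyses in section 1, and section 7.10), so it should not carry two thresholds for lowering the dose.

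**Working it through.** **1. Which rule do the plan's own numbers assume?**

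Inputs: about 110 randomised, 2 already treated in Cohort 1, 3~6 per palbociclib dose level, 3~24 per cohort, 115~136 treated in total (SAP 5 and Protocol 10.1); four Cohort 2 dose levels (SAP 6.2).

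- Stated minimum: 110 + 2 + 3 = 115. Reproduced.
- Stated maximum: 110 + 2 + 4 × 6 = 136. Reproduced.
- Any-DLT rule applied literally at every level: no level goes beyond 3 evaluable participants, so the maximum is 110 + 2 + 4 × 3 = 124.
- Any-DLT rule applied only at the starting level, with full 3 + 3 at the three lower levels: 110 + 2 + 3 + 3 × 6 = 133.

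Like the plan's own 3~6, these counts ignore replacement of non-evaluable participants. Only the branches, with expansion to 6 at every level, give 136. The branches are the intended rule and the any-DLT sentence is the error.

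**2. Where do the two rules diverge at one dose level?**

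| Result | Any-DLT sentence | Branches (SAP 2.2 and Protocol 5.1.2.1) |
|---|---|---|
| 0 of 3 | not triggered | proceed at this dose |
| 1 of 3 | lower dose | expand to 6 at the same dose |
| 1 of 6 | lower dose | proceed at this dose |
| 2 or more of 6 | lower dose | lower dose |
| 2 or 3 of 3 | lower dose | not stated in the visible text |

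The first action differs at 1 of 3. Among the outcomes that the branches cover, the dose decision differs only at 1 of 6. If the expansion brings a further DLT, both routes end at a lower dose.

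**3. How often would that arise?**

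The visible text gives no DLT rate, so the true 4-week rate p is assumed and outcomes are taken as independent.

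- First action differs: P(1 of 3) = 3p(1 − p)².
- Dose decision differs: P(1 of 3, then 0 of the next 3) = 3p(1 − p)² × (1 − p)³ = 3p(1 − p)⁵.

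| Assumed p | First action differs | Dose decision differs |
|---|---|---|
| 5% | 13.5% | 11.6% |
| 10% | 3 × 0.1 × 0.81 = 24.3% | 0.243 × 0.729 = 17.7% |
| 20% | 3 × 0.2 × 0.64 = 38.4% | 0.384 × 0.512 = 19.7% |
| 30% | 3 × 0.3 × 0.49 = 44.1% | 0.441 × 0.343 = 15.1% |
| 50% | 37.5% | 4.7% |

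The first column peaks at p = 1/3, at 4/9 = 44.4%. The second peaks at p = 1/6, at 3 × (1/6) × (5/6)⁵ = 20.1%.

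**The case against.** The best defence is that the sentence is a clumsy lead-in. It refers to a 3 + 3 schema, the next sentences spell that schema out, and those details match the protocol and the planned 3~6 per level, so a careful reader can recover the intended rule from the SAP alone. It also sits in the study description. SAP 7.6.1 only summarises and lists DLTs, and neither the DLT-evaluable population nor the outputs in SAP 7.10 use the any-DLT trigger. Conduct rests with the protocol, where expansion and de-escalation are settled at a dose decision meeting of investigators and sponsor personnel, and: "Drug administration at the next dose level or proceeding to the Randomized Phase must not occur until the Investigator receives written confirmation from BMS".

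Most of this stands, and it keeps the impact low. It does not make the sentence right, because a lead-in to 3 + 3 would not attach a lower dose to a single DLT.

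Three stronger readings are tempting and are not supported:

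- **A nivolumab conflict.** A reader might infer that naming palbociclib contradicts the protocol's rule: "If a cohort is discontinued due to DLT related to nivolumab, a different dose or dose schedule will be explored". The protocol's general default, for DLTs of unclear relevance to nivolumab, is a lower CDK4/6 inhibitor dose, and SAP 6.2 keeps nivolumab at 480 mg in every Cohort 2 level. The SAP sentence abbreviates that default and leaves out the exception.
- **Agreement at 2 or 3 of 3.** A reader might assume that both rules lower the dose there. That is ordinary 3 + 3 practice, but the branches in the visible text of both documents do not cover it. Protocol Figure 5.1.2.1-1 may; it is not shown.
- **24% to 44% as the risk of a wrong dose.** Those figures are the chance that the conflicting text becomes relevant. The dose decision differs less often, and the sponsor's confirmation stands between the text and any action.

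**Conclusion.** The point holds as a wrong decision threshold in current SAP text. The contradiction is visible on the page and needs no assumed rate. The plan's maximum of 136, against 124 under a literal any-DLT rule, shows that the branches are what was meant.

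At assumed true DLT rates of 10% to 30%, the two instructions differ on the first action in 24.3% to 44.1% of cases, and on the dose decision in about 15% to 20%. The percentages rest on the assumed rates, independent outcomes and 3 evaluable participants at the start. They describe the two texts, not the likelihood of an actual dosing error.

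The correction is worth making but low in impact. The protocol is clear and governs conduct, and the RCB 0-I analysis does not change.

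**What to change.** Change the trigger in that SAP 2.2 sentence from any DLT to two or more DLT-evaluable participants with a DLT at a dose level. It then fits the 1-of-3, 1-of-6 and 2-of-6 branches and still covers 2 or 3 of 3. Alternatively, replace the sentence with a pointer to Protocol 5.1.2.1 and its schematic.

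Plain deletion is the weaker option. It would clear the contradiction but also remove the only visible SAP sentence that reaches 2 or 3 of 3.

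The cost is one sentence in the SAP. No protocol amendment, added participants, changed analysis or delay follows from it.

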**Table 2.2-1: Abemaciclib Dose Modifications for Adverse Reactions**

Dose Level	Abemaciclib Dose Combination with an Aromatase Inhibitor
Recommended starting dose	150 mg BID
First dose reduction	100 mg BID
Second dose reduction	50 mg BID
Third dose reduction	NA

Abbreviations: BID = twice daily; NA = not applicable.

The dose modifications permitted for palbociclib in combination with anastrozole are based on the dose level changes outlined in [Table 2.2-2](#).

